9.1.9 Subject Pregnancy

Women of child-bearing potential are not excluded from the study. However, if a woman becomes pregnant during the study, S&N must be contacted immediately once the investigator is made aware of the pregnancy and a decision will be made regarding the continuation in the study of the pregnant woman. Pregnancy is not reportable as an adverse event; however, complications related to the pregnancy may be reportable as determined on a case-by-case basis. Pregnancy-related information will be collected until the end of the pregnancy.

9.2 STUDY METHODS AND MEASUREMENTS

9.2.1 Pressure Ulcer Classification

Pressure ulcers should be classified according to the European Pressure Ulcer Advisory Panel 2017 (3).

Stage I: Non-blanchable erythema

Intact skin with non-blanchable redness of a localized area usually over a bony prominence. Darkly pigmented skin may not have visible blanching; its color may differ from the surrounding area. The area may be painful, firm, soft, warmer or cooler as compared to adjacent tissue. Category I may be difficult to detect in individuals with dark skin tones. May indicate “at risk” persons.

Stage II: Partial-thickness

Partial thickness loss of dermis presenting as a shallow open ulcer with a red pink wound bed, without slough. May also present as an intact or open/ruptured serum-filled blister. Presents as a shiny or dry shallow ulcer without slough or bruising.* This Category/Stage should not be used to describe skin tears, tape burns, perineal dermatitis, maceration or excoriation.

*Bruising indicates suspected deep tissue injury.

Stage III: Full-thickness skin loss

CONFIDENTIAL AND PROPRIETARY

This document contains information that is confidential and proprietary to Smith & Nephew PLC and Smith & Nephew, Inc. and is intended for use only by Smith & Nephew and its manufacturer. It shall not be reproduced or copied in whole or in part, nor shall the contents be disclosed by any means without prior written permission from Smith & Nephew, nor shall anyone make any use of it that is contrary to the expressed or implied wishes of Smith & Nephew.

| | |
|--|---|
| Study Protocol—Device |  |
| A Prospective, Multi-center, Post-Market Clinical Follow-Up Study to Evaluate the Safety and Effectiveness of ALLEVYN Gentle Border | Number: ALLEV.PMCF.2017.13 |
| | Version: 3.0 |
| | Date: 21 JUN 2019 |
| | Page: Page 42 of 90 |

Full thickness tissue loss. Subcutaneous fat may be visible but bone, tendon or muscle are not exposed. Slough may be present but does not obscure the depth of tissue loss. May include undermining and tunneling. The depth of a Category/Stage III pressure ulcer varies by anatomical location. The bridge of the nose, ear, occiput and malleolus do not have subcutaneous tissue and Category/Stage III ulcers can be shallow. In contrast, areas of significant adiposity can develop extremely deep Category/Stage III pressure ulcers. Bone/tendon is not visible or directly palpable.

Stage IV: Full thickness tissue loss

Full thickness tissue loss with exposed bone, tendon or muscle. Slough or eschar may be present on some parts of the wound bed. Often include undermining and tunneling. The depth of a Category/Stage IV pressure ulcer varies by anatomical location. The bridge of the nose, ear, occiput and malleolus do not have subcutaneous tissue and these ulcers can be shallow. Category/Stage IV ulcers can extend into muscle and/or supporting structures (e.g., fascia, tendon or joint capsule) making osteomyelitis possible. Exposed bone/tendon is visible or directly palpable.

9.2.2 Diabetic Foot Ulcer (DFU) Classification

Diabetic foot ulcers should be classified according to SINBAD assessment (5). The SINBAD score represents an ulcer classification system which can be used as a standard measure in international studies. The SINBAD score ranges from 0 to 6 and emphasizes 6 different elements for DFU classification. The higher the score the higher the grade of DFU. The SINBAD score will be assessed for each subject at baseline visit.

- Site 0=Forefoot
 1=Midfoot and Hind Foot
- Ischemia 0=Pedal blood flow intact
 1=Reduced pedal blood flow
- Neuropathy 0=Sensation intact
 1=Sensation lost

CONFIDENTIAL AND PROPRIETARY

This document contains information that is confidential and proprietary to Smith & Nephew PLC and Smith & Nephew, Inc. and is intended for use only by Smith & Nephew and its manufacturer. It shall not be reproduced or copied in whole or in part, nor shall the contents be disclosed by any means without prior written permission from Smith & Nephew, nor shall anyone make any use of it that is contrary to the expressed or implied wishes of Smith & Nephew.

| | |
|--|---|
| Study Protocol—Device |  |
| A Prospective, Multi-center, Post-Market Clinical Follow-Up Study to Evaluate the Safety and Effectiveness of ALLEVYN Gentle Border | Number: ALLEV.PMCF.2017.13 |
| | Version: 3.0 |
| | Date: 21 JUN 2019 |
| | Page: Page 43 of 90 |

Infection 0=None (bacterial)
 1=Present

Area 0=Ulcer< 1cm²
 1=Ulcer> 1cm²

Depth 0=Ulcer confined to skin and subcutaneous tissue
 1=Ulcer reaching muscle, tendon or deeper

9.2.3 Photographs and Wound Size Measurements

The primary endpoint will be assessed by the wound photographs collected by the delivered digital camera (Silhouette) during each key study visit. This makes sure that photographs can be compared by using a standardized technique. The secondary endpoint information will be derived by the following investigator assessments and by patient questionnaires as listed in this section below.

Photographs:

Wound photographs will be done by the investigator or delegated personnel. Photographs will be taken for all subjects per visit instructions (see section 9.1) by using the delivered digital camera (Silhouette). The study centers will be trained on the use of the camera prior to start with patient enrolment.

Wound Size Measurement:

The wound size measurements will be performed directly from the wound photographs taken from the wound per each visit. A special digital camera (Silhouette, ARANZ) will be delivered to the study center. The camera will measure the lengths, the depth and the width of the wound automatically. The wound photographs and the resulting wound measures will be stored in a database. A training will be performed prior to start of the study and handling instructions will be provided.

CONFIDENTIAL AND PROPRIETARY

This document contains information that is confidential and proprietary to Smith & Nephew PLC and Smith & Nephew, Inc. and is intended for use only by Smith & Nephew and its manufacturer. It shall not be reproduced or copied in whole or in part, nor shall the contents be disclosed by any means without prior written permission from Smith & Nephew, nor shall anyone make any use of it that is contrary to the expressed or implied wishes of Smith & Nephew.

| | |
|--|---|
| Study Protocol—Device |  |
| A Prospective, Multi-center, Post-Market Clinical Follow-Up Study to Evaluate the Safety and Effectiveness of ALLEVYN Gentle Border | Number: ALLEV.PMCF.2017.13 |
| | Version: 3.0 |
| | Date: 21 JUN 2019 |
| | Page: Page 44 of 90 |

9.2.4 Reference Wound Assessments with modified Bates-Jensen Wound Assessment Tool (BWAT)

Wound assessments will be performed by the investigator at each study visit in alignment with the Bates-Jensen Wound Assessment Tool (4). The Bates-Jensen Wound Assessment Tool provides 13 assessment parameters which will be scored in a defined measure (1). Each score items will be summarized into a total score. The higher the total score, the more severe the wound status. A source data sheet containing each listed score items will be provided to the study centers to document the BWAT on a primary source. The BWAT tool and the instructions can be found in Appendix 21.4.

9.2.5 Patient Assessment Scale

The patient assessment scale (PAS) is a questionnaire that will be filled out by the patient. During the AGB treatment phase, the subject will be asked to answer the following questions at each study visit. The PAS will be entered directly into the case report form and will serve as source data.

1. How have you found your experience in terms of leakage?
0=Unacceptable level of leakage
10=No leakage
2. How have you found your experience in terms of the feeling of moisture on your skin underneath the dressing
0=Unacceptable feeling of moisture
10=No feeling of moisture on the skin
3. How have you found your experience in terms of odour?
0=Unacceptable level of odour
10=No odour
4. How have you found your experience in terms of visible exudate?
0=Unacceptable level of visible exudate
10=No visible exudate

CONFIDENTIAL AND PROPRIETARY

This document contains information that is confidential and proprietary to Smith & Nephew PLC and Smith & Nephew, Inc. and is intended for use only by Smith & Nephew and its manufacturer. It shall not be reproduced or copied in whole or in part, nor shall the contents be disclosed by any means without prior written permission from Smith & Nephew, nor shall anyone make any use of it that is contrary to the expressed or implied wishes of Smith & Nephew.

| | |
|--|---|
| Study Protocol—Device |  |
| A Prospective, Multi-center, Post-Market Clinical Follow-Up Study to Evaluate the Safety and Effectiveness of ALLEVYN Gentle Border | Number: ALLEV.PMCF.2017.13 |
| | Version: 3.0 |
| | Date: 21 JUN 2019 |
| | Page: Page 45 of 90 |

5. How protected did the dressing make your wound feel?
0=Unacceptable level of protection
10=Very protected
6. How have you found your experience in terms of dressing comfort?
0=Unacceptable level of comfort
10=Very comfortable
7. How have you found your experience in terms of being able to maintain a normal showering routine? (NA if patient does not have a normal showering routine)
0=Unacceptable level of impact (unable to bathe)
10=No negative impact

9.2.6 Patient Pain Scale (PPS)

During the AGB treatment phase, the patient will be asked to describe the level of pain during the application, during AGB treatment and on removal of the dressing on a scale from 0 (no pain) to 10 (worst pain). The subject will be asked to draw a vertical line on this visual scale to indicate the value. The value will be rounded to a whole number and transmitted into the CRF by the investigator. The PPS will be entered directly into the case report form and will serve as source data.

CONFIDENTIAL AND PROPRIETARY

[figure not shown]
This document contains information that is confidential and proprietary to Smith & Nephew PLC and Smith & Nephew, Inc. and is intended for use only by Smith & Nephew and its manufacturer. It shall not be reproduced or copied in whole or in part, nor shall the contents be disclosed by any means without prior written permission from Smith & Nephew, nor shall anyone make any use of it that is contrary to the expressed or implied wishes of Smith & Nephew.

| | |
|--|---|
| Study Protocol—Device |  |
| A Prospective, Multi-center, Post-Market Clinical Follow-Up Study to Evaluate the Safety and Effectiveness of ALLEVYN Gentle Border | Number: ALLEV.PMCF.2017.13 |
| | Version: 3.0 |
| | Date: 21 JUN 2019 |
| | Page: Page 46 of 90 |

[figure not shown]
Level of pain experienced by the subject on application of the dressing

Level of pain experienced by the subject during treatment with AGB

Level of pain experienced by the subject on removal of the dressing

9.2.7 Cardiff Wound Impact Questionnaire (CWIS)

The CWIS is a Quality of Life Questionnaire. During the AGB treatment phase, the subject will be asked to fill out the CWIS at each study visit. The CWIS will be entered directly into the case report form and will serve as source data.

The CWIS is a subjective, qualitative measure that covers four domains: physical functional status, symptoms and side effects, social functioning and psychological state. Each line item provides 5 answers. Only one box should be ticked by the subject per line item. The 5-point Likert scale will be counted from 1 to 5 and each domain will be listed separately at the end of the study (6).

1 = Not at all/Not Applicable, 2 = Slightly, 3 = Moderately, 4 = Quite a bit, and 5 = Very

9.2.8 Dressing and Clinical Performance

The following items on dressing and clinical performance will be assessed by the investigator at each study visit.

CONFIDENTIAL AND PROPRIETARY

This document contains information that is confidential and proprietary to Smith & Nephew PLC and Smith & Nephew, Inc. and is intended for use only by Smith & Nephew and its manufacturer. It shall not be reproduced or copied in whole or in part, nor shall the contents be disclosed by any means without prior written permission from Smith & Nephew, nor shall anyone make any use of it that is contrary to the expressed or implied wishes of Smith & Nephew.

| | |
|--|---|
| Study Protocol—Device |  |
| A Prospective, Multi-center, Post-Market Clinical Follow-Up Study to Evaluate the Safety and Effectiveness of ALLEVYN Gentle Border | Number: ALLEV.PMCF.2017.13 |
| | Version: 3.0 |
| | Date: 21 JUN 2019 |
| | Page: Page 47 of 90 |

- Healing of reference wound (yes/no) and signs of clinical infection.
- Dressing comfort (wear comfort, showerproof qualities, odour control)
- Dressing movement (reason for change, adherence to wound, dressing retention, dressing lift or bunching up)
- Dressing performance (leakage, strikethrough, change frequency, wear time, fluid handling ability)
- Exudate evaluation (type, amount, viscosity)
- Pain evaluation (application, during treatment, removal)
- Wound and surrounding skin evaluation

9.2.9 Biological Samples

This study does not require the collection of any biological samples.

9.3 QUALITY OF LIFE

The CWIS is a Quality of Life Questionnaire. During the AGB treatment phase, the subject will be asked to fill out the CWIS at each key study visit.

The Cardiff Wound Impact Schedule (CWIS) is a validated tool for assessing the health-related quality of life of people with venous leg ulcers and diabetic foot ulcers. It is a subjective, qualitative measure that covers three domains:

- Physical symptoms and daily living (24 items, score range: 24-120)
- Social life (14 items, score range: 14-70)
- Well-being (7 items, score range: 7-35)

Each question provides 5 answers and will be counted from 1 (not at all) to 5 (very). Only one box should be ticked by the subject per line item. (6). This instrument also includes two further single item 'global' scales for HRQoL and satisfaction with the quality of life.

CONFIDENTIAL AND PROPRIETARY

This document contains information that is confidential and proprietary to Smith & Nephew PLC and Smith & Nephew, Inc. and is intended for use only by Smith & Nephew and its manufacturer. It shall not be reproduced or copied in whole or in part, nor shall the contents be disclosed by any means without prior written permission from Smith & Nephew, nor shall anyone make any use of it that is contrary to the expressed or implied wishes of Smith & Nephew.

| | |
|--|---|
| Study Protocol—Device |  |
| A Prospective, Multi-center, Post-Market Clinical Follow-Up Study to Evaluate the Safety and Effectiveness of ALLEVYN Gentle Border | Number: ALLEV.PMCF.2017.13 |
| | Version: 3.0 |
| | Date: 21 JUN 2019 |
| | Page: Page 48 of 90 |

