| Informed Consent | √ | | | | | | |
| Demographics/ Medical History | √ | | | | | | |
| Verify Inclusion/ Exclusion Criteria | √ | | | | | | |
| Allocate Study ID Number | √ | | | | | | |
| Concomitant Medication | √ | √ | √ | √ | √ | √ | √ |
| CWIS Patient Questionnaire | √ | √ | √ | √ | √ | | √ |
| Patient Pain Scale | √ | √ | √ | √ | √ | √ | |
| Patient Assessment | | √ | √ | √ | √ | √ | |
| Wound Assessment | √ | √ | √ | √ | √ | √ | √ |
| Photograph Dressing in situ Before Removal | | √ | √ | √ | √ | √ | √ |
| Dressing Change | | √ | √ | √ | | √ | |
| Photograph Wound Before Dressing Application | √ | √ | √ | √ | √ | √ | √ |
| Dressing Performance | √ | √ | √ | √ | √ | √ | |

CONFIDENTIAL AND PROPRIETARY

This document contains information that is confidential and proprietary to Smith & Nephew PLC and Smith & Nephew, Inc. and is intended for use only by Smith & Nephew and its manufacturer. It shall not be reproduced or copied in whole or in part, nor shall the contents be disclosed by any means without prior written permission from Smith & Nephew, nor shall anyone make any use of it that is contrary to the expressed or implied wishes of Smith & Nephew.

| | |
|--|---|
| Study Protocol—Device |  |
| A Prospective, Multi-center, Post-Market Clinical Follow-Up Study to Evaluate the Safety and Effectiveness of ALLEVYN Gentle Border | Number: ALLEV.PMCF.2017.13 |
| | Version: 3.0 |
| | Date: 21 JUN 2019 |
| Page: Page 9 of 90 | |

| Schedule of Events | Key Visits | | | | | Other Visits | |
|---------------------------------|-----------------------|-----------------|------------------|------------------|-------------------------|--------------------------------|--|
| | Visit 1 (Baseline) | Visit 2 | Visit 3 | Visit 4 | End of Study Visit 5 | Routine Dressing Changes | Treatment Discontinuation (before end of study) |
| | Day 0 | Day 7 (+/-3) | Day 14 (+/-3) | Day 21 (+/-3) | Day 28 (+/-3) | | |
| Adverse Event (AE) Assessment | √ | √ | √ | √ | √ | √ | √ |
| Record Device Deficiencies (DD) | √ | √ | √ | √ | √ | √ | √ |
| End of Study /Exit Form | | | | | √ | | √ |

CONFIDENTIAL AND PROPRIETARY

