| 11. Record the total time that the subject spent at the visit (start to finish of wound care procedures). |
|---|

9.1.3 Study Visit 2 (day 7, ±3), Visit 3 (day 14, ±3), Visit 4 (day 21, ±3)

Visits 2 - 4 will be performed as on-site visits, so the subjects need to be present at each key study time point. These visits should take place every seventh (7) day. In case a dressing change is required before day 7, the instructions for a Routine Dressing Change Visit need to be followed (chapter 9.1.4).

Subjects who are already withdrawn from treatment and no longer require a dressing change shall be followed up on the study visits to collect safety information.

- | |
|---|
| 
 1. Question subjects regarding any changes in health or concomitant treatment. 2. Hand out the CWIS, Patient Assessment Scale and Pain Scale to the subject and allow sufficient time to complete it. 3. Photograph the dressing in situ prior to removal with the delivered digital camera. 4. Remove the old dressing and inspect the wound. Complete a wound assessment according to BWAT (see Section 9.2.4). 5. Assess the reason for dressing change, assess the ease of dressing removal and dressing leakage. 6. Record any debridement and the method of debridement, and take a photograph of the wound immediately prior to and following debridement. Note: Photographs are not necessary if the subject was withdrawn from treatment at a previous visit. 7. Redress the wound, if clinically indicated. 8. Record details of all dressings used (e.g. brand, size, etc.) as well as any treatment applied underneath the dressing. |
|---|

CONFIDENTIAL AND PROPRIETARY

This document contains information that is confidential and proprietary to Smith & Nephew PLC and Smith & Nephew, Inc. and is intended for use only by Smith & Nephew and its manufacturer. It shall not be reproduced or copied in whole or in part, nor shall the contents be disclosed by any means without prior written permission from Smith & Nephew, nor shall anyone make any use of it that is contrary to the expressed or implied wishes of Smith & Nephew.

| | |
|--|---|
| Study Protocol—Device |  |
| A Prospective, Multi-center, Post-Market Clinical Follow-Up Study to Evaluate the Safety and Effectiveness of ALLEVYN Gentle Border | Number: ALLEV.PMCF.2017.13 |
| | Version: 3.0 |
| | Date: 21 JUN 2019 |
| | Page: Page 37 of 90 |

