9.1.5 End of Study Visit (day 28, ±3)

The End of Study Visit will be performed as an on-site visit. This should coincide with the normal timing of dressing changes, i.e. seven (7) days.

1. Question subjects regarding any changes in health or concomitant treatment.
2. Hand out the CWIS, Patient Assessment Scale and Pain Scale to the subject and allow sufficient time to complete it.
3. Photograph the dressing in situ prior to removal with the delivered digital camera.
4. Remove the old dressing, inspect the wound and complete wound assessment according to BWAT (see Section 9.2.4).
Note: A full wound assessment is not necessary if the subject has already been withdrawn from treatment.
5. Assess the reason for dressing change, assess the ease of dressing removal and dressing leakage.
6. Record any debridement and the method of debridement, and **take a photograph of the wound immediately prior to and following debridement.**
7. Fill out the Study Completion CRF.

CONFIDENTIAL AND PROPRIETARY

This document contains information that is confidential and proprietary to Smith & Nephew PLC and Smith & Nephew, Inc. and is intended for use only by Smith & Nephew and its manufacturer. It shall not be reproduced or copied in whole or in part, nor shall the contents be disclosed by any means without prior written permission from Smith & Nephew, nor shall anyone make any use of it that is contrary to the expressed or implied wishes of Smith & Nephew.

| | |
|--|---|
| Study Protocol—Device |  |
| A Prospective, Multi-center, Post-Market Clinical Follow-Up Study to Evaluate the Safety and Effectiveness of ALLEVYN Gentle Border | Number: ALLEV.PMCF.2017.13 |
| | Version: 3.0 |
| | Date: 21 JUN 2019 |
| | Page: Page 39 of 90 |

- | |
|---|
| 
8. Record the total time that the subject spent at the visit (start to finish of wound care procedures).
 
9. If any AE or DD are observed or reported, they must be recorded as instructed in Safety Section 12.
 |
|---|

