10.4.2 Analysis of Secondary Endpoints

All secondary endpoints will be analysed using the mITT population as the primary analysis.

Wound Measurements

The reference wound volume and depth will be summarised at each dressing change assessment and study visit. The absolute reduction in the reference wound volume and depth from baseline to each visit will also be summarised.

The same analysis as the above repeated ANCOVA model is planned to be used to analyse absolute reduction in volume and depth (separately) from baseline to all post-baseline study visits. As well as the summaries of absolute reduction, the percentage reduction in area, volume and depth will also be summarised from baseline to all post-baseline study visits.

Cardiff Wound Impact Schedule (CWIS):

The CWIS consists of three domains: Social Life (CWIS-SL), Wellbeing (CWIS-WB), Physical Symptoms and Daily Living (CWIS-PSDL). For each domain a score from 0-100 is derived with higher scores being better.

Scores for each CWIS domain will be summarised at each study visit by wound type and overall. The increase in score from baseline to each study visit will also be summarised by wound type and overall.

A repeated measures ANCOVA model will be fit separately for each CWIS domain. In each case the domain score will be used as the dependent variable and as a minimum the model will contain a term for visit. The following extra terms will be added to the model using a stepwise selection procedure with an F-value to attain a significance level of 0.1: centre, wound type, BMI and baseline domain score. The estimate LSMean increase in domain score from baseline to all study visits will be presented with the associated 95% confidence intervals.

If the assumptions of ANCOVA are not met then a non-parametric analysis will be considered.

CONFIDENTIAL AND PROPRIETARY

This document contains information that is confidential and proprietary to Smith & Nephew PLC and Smith & Nephew, Inc. and is intended for use only by Smith & Nephew and its manufacturer. It shall not be reproduced or copied in whole or in part, nor shall the contents be disclosed by any means without prior written permission from Smith & Nephew, nor shall anyone make any use of it that is contrary to the expressed or implied wishes of Smith & Nephew.

| | |
|--|---|
| Study Protocol—Device |  |

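### The documents conflict on whether the CWIS continues after AGB treatment stops, and a site following the restrictive text would lose later scores for reasons tied to outcome

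*Combined protocol and SAP*

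**What the plan says.** Two sections tie the questionnaire to treatment. Section 9.2.7 reads "During the AGB treatment phase, the subject will be asked to fill out the CWIS at each study visit", and 9.3 repeats the sentence for key visits: "During the AGB treatment phase, the subject will be asked to fill out the CWIS at each key study visit". Three further sections describe what happens after a subject is withdrawn from AGB. Sections 7.8.1 and 9.1.1 keep the subject coming to day 28 or Visit 5 with safety as the stated purpose. Section 9.1.3 says that subjects withdrawn from treatment who need no further dressing change "shall be followed up on the study visits to collect safety information". Section 7.8.1 lists wound closure, worsening, an adverse event and a clinically warranted change of treatment among the possible reasons for withdrawal.

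Other current text carries no such limit. In Table 1 the row "CWIS Patient Questionnaire" is ticked at Visits 1 to 5 and in the Treatment Discontinuation column. Step 2 for Visits 2 to 4 (9.1.3) and step 2 of the End of Study Visit (9.1.5) both say "Hand out the CWIS, Patient Assessment Scale and Pain Scale to the subject and allow sufficient time to complete it".

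For analysis, 10.4.2 fits a repeated measures ANCOVA to each CWIS domain in the mITT population, and "The estimate LSMean increase in domain score from baseline to all study visits will be presented with the associated 95% confidence intervals". It also plans plain summaries of score and of change from baseline at each visit. Section 10.1 leaves the handling of missing data to the SAP. The supplied text contains no rule for a score that is missing because treatment ended.

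**The concern.** The CWIS change from baseline is the named patient-reported endpoint. If collection stops when AGB stops, scores go missing for some of the subjects who did best (closed wound) and some of those who did worst (worsening, reaction, switch). Whether a score exists would then depend on how the wound fared.

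The CWIS asks about the effect of the wound on the patient's life and does not need the dressing to be in place. Its form even has a box for a healed wound (Appendix 21.5). The same treatment-phase phrase in 9.2.5 and 9.2.6 is easier to understand, because those scales mostly rate the dressing. Since 9.1.1 keeps these subjects coming to the key visits, the data would be lost only for want of handing out a form.

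**Working it through.** The plan gives no figure for the CWIS. Its power statements concern wound area and do not bear on this point. The check is therefore a comparison of the passages, followed by an illustration of what a gap could do.

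**Passages side by side**

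| Source | CWIS after AGB has stopped? |
|---|---|
| 9.2.7, 9.3 | Not requested: tied to the treatment phase |
| 7.8.1, 9.1.1 | Visits continue; stated purpose is safety; CWIS not mentioned |
| 9.1.3, opening text | Safety information, for subjects needing no further dressing change |
| Table 1 | Ticked at Visits 1-5 and at Treatment Discontinuation |
| 9.1.3 step 2, 9.1.5 step 2 | Handed out; no exemption for subjects off treatment |

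The step lists do make exemptions elsewhere. For Visits 2 to 4: "Photographs are not necessary if the subject was withdrawn from treatment at a previous visit". For the End of Study Visit: "A full wound assessment is not necessary if the subject has already been withdrawn from treatment". Neither covers the CWIS. The two groups of passages give a site different answers, and nothing says which prevails.

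**What the Treatment Discontinuation score can do.** Under Table 1, a subject who stops early should have a last CWIS. The Social Life items, the Physical Symptoms items and the overall ratings look back over 7 days. A score taken on the day of closure or of a switch therefore largely describes the time before it, and cannot stand for day 28.

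**Effect on the raw day-28 mean.** Let f be the share without a day-28 score, and D the mean change of those subjects minus the mean change O of the subjects with a score.

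- Full-cohort mean = (1 - f) x O + f x (O + D) = O + f x D
- Observed mean - full-cohort mean = -f x D

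The documents give neither f nor D. The values below are assumptions, on the 0-100 domain scale, with 40 subjects and no other losses.

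| f | Subjects with a day-28 score | Shift if D = +10 | Shift if D = -10 |
|---|---|---|---|
| 10% | 36 | -1.0 | +1.0 |
| 20% | 32 | -2.0 | +2.0 |
| 30% | 28 | -3.0 | +3.0 |
| 40% | 24 | -4.0 | +4.0 |

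With D = 20 and f = 30%, the shift is 0.30 x 20 = 6 points.

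If a share c is missing after closure (difference +D) and a share s after treatment failure (difference -D), the shift is -(c - s) x D. With D = 10:

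- c = 20%, s = 10%: -1.0
- c = 10%, s = 20%: +1.0
- c = s = 15%: 0

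The sign is therefore open, and the two kinds of loss can cancel.

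**Effect on the LSMeans.** The formula does not apply to the model estimate. If the model is fitted to all available visits, subjects with earlier scores still contribute, and the day-28 LSMean is distorted only to the extent that the missing scores cannot be predicted from earlier scores and the covariates. That assumption is doubtful once a wound has closed or been re-treated, but the documents offer no means of testing it.

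**The case against.** The strongest reply is that the plan already intends collection to day 28. Table 1 and both step lists say so, and where subjects off treatment are excused from something, the text names it. Section 9.1.1 counts them as active participants. The phrase in 9.2.7 and 9.3 cannot be wholly literal: at Visit 1 the CWIS (step 4) comes before the first dressing (step 7), so a strict reading would exclude the baseline score. The phrase may simply mean the four-week study period. The safety wording states a purpose and does not prohibit other data.

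Much of this stands. A reader might infer that the plan has settled on stopping the CWIS with treatment, and that the reported quality-of-life change will therefore come from a selected group. The documents do not support that. The restriction is contradicted by other current text, and withdrawal on closure is at the investigator's discretion (7.8.1). The 3 cm² minimum was added so that wounds could be assessed over four weeks (21.1.2), and the mITT model is not limited to subjects with a day-28 score.

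What does not fall away is the conflict itself. Five sections can be read as permission to stop. Section 6.1.1 makes treatment duration depend partly on healing, so early stops for closure are foreseen. Leaving missing data to the SAP does not help, because no analysis replaces a questionnaire that was not handed out.

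On-treatment measurement could also be defended, since scores after a switch partly reflect another treatment. That is a reason to report treatment status alongside the scores. It does not justify leaving the instruction ambiguous.

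**Conclusion.** The concern holds as a contradiction in the collection rules that carries a risk of outcome-related missing CWIS scores. If sites follow 9.2.7, 9.3 and the safety-only wording, the visit summaries would describe only the subjects still on AGB, and the LSMeans would lean on an untested missing-data assumption. If sites follow Table 1 and the step lists, the problem does not arise.

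The size and direction of any bias cannot be determined from the documents. The figures of 1 to 4 points, or 6 at the extreme shown, rest entirely on assumed inputs, apply to the raw mean only, and can be zero when closures and failures offset each other. The endpoint is secondary and carries no power claim. The correction is still worth making because it is cheap and must precede the visits it affects.

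**What to change.** 1. In 9.2.7 and 9.3, remove the limit to the treatment phase and state that the CWIS is completed at every key visit to day 28, whether or not the subject is still treated with AGB. This agrees with Table 1 and with step 2 of 9.1.3 and 9.1.5.
2. In 7.8.1, 9.1.1 and 9.1.3, add the CWIS to what is collected after withdrawal from treatment, alongside safety.
3. In 10.4.2 or the SAP, state that these scores enter the mITT CWIS model, and that the Treatment Discontinuation score is not used in place of the day-28 score.
4. Report the number of subjects off AGB at each visit next to the CWIS results.

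The cost is a wording change in these sections and one questionnaire of about ten minutes (the form's own estimate) at visits these subjects already attend. The drawback is that scores after a switch partly reflect another treatment; item 4 makes that visible. The change concerns data collection only and leaves the rules for stopping treatment untouched.
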